1. INTRODUCTION

1.1 Disease Background

Prostate cancer is the second leading cause of cancer deaths in men. According to American Cancer Society estimates, in 2016 as many as 180,890 American men will be diagnosed with prostate cancer, and nearly 26,120 will die of the disease.² Yet, localized prostate carcinoma is often curable, and even metastatic disease frequently responds to treatment.

The course of prostate cancer from diagnosis to death is best categorized as a series of clinical states defined by the status of the primary tumor, the presence or absence of distant disease (metastatic versus non-metastatic), testosterone levels, and the lines of therapy a patient has received (Figure 1).³ These clinical states involve the complex interplay of a network of signaling molecules that collectively promote net cell proliferation relative to cell death. The clinical states model aligns with the indications and uses of currently approved drugs and provides a framework for a decision tree that closely follows contemporary clinical practice.

Figure 1. Clinical states of prostate cancer

[figure not shown]
Although advanced prostate cancer usually responds to therapies that suppress androgen-axis signaling, resistance inevitably develops, leading to the emergence of castration-resistant prostate cancer (CRPC). Importantly, the clinical efficacy of novel therapies targeting androgen receptor (AR) signaling, such as abiraterone and enzalutamide, have confirmed that most CRPC remains AR signaling intact.⁴⁻⁶ Since resistance to these therapies inevitably develops, approaches to improve the duration of response and address the key pathways of resistance are very much needed.

Despite promising early phase clinical trial results,⁷ a recently presented Phase III trial evaluating the multi-tyrosine kinase inhibitor (MTKI) cabozantinib in CRPC did not meet its primary survival endpoint.⁸ Although the AR signaling status was unknown in trial participants, the majority of men with CRPC retain active AR signaling.^{9,10} Our preclinical study provided a mechanistic basis and rationale of combining cabozantinib with enzalutamide to co-target the MET kinase and AR respectively and, furthermore, provided a potential explanation for the failure of cabozantinib monotherapy in the pivotal Phase III study.¹¹

In a search for alternate MTKIs that could be re-positioned for the treatment of metastatic CRPC (mCRPC), we synthesized and evaluated ESK981 amongst a panel of other MTKIs. Interestingly, as our preliminary data will highlight, ESK981 exhibited nanomolar activity in the inhibition of prostate cancer cell line growth relative to other MTKIs tested including cabozantinib and crizotinib (both of which have been evaluated clinically in mCRPC). These early results piqued our further interest in deciphering the molecular basis for the log-fold increased sensitivity to ESK981 relative to other MTKIs in prostate cancer cells.

ESK981 is an orally active multiplex kinase inhibitor with favorable safety, pharmaceutical, ADME (absorption, distribution, metabolism, and excretion), and pharmacokinetic profiles. Clinical testing demonstrated linear dose-related oral exposure in humans with 8-15 h half-life and a high level of patients achieving stable disease at doses at or right below the expected Phase II dose. Our observation of a direct activity of ESK981 on prostate cancer cell autophagy coupled with its anti-angiogenesis activities provides a compelling rationale to investigate this MTKI in the treatment of mCRPC patients.

1.2 Treatment Background

ESK981, formerly known as CEP-11981, is a novel oral MTKI originally developed by Cephalon¹² and currently being developed by Esanik Therapeutics. The compound was initially identified as an oral angiogenesis inhibitor targeting several important pathways involved in the angiogenic response, but without the off-target activities of other TKIs, like sunitinib and sorafenib, resulting in adverse events. ESK981 has potent activity in kinases implicated in angiogenesis including vascular endothelial growth factor receptor 1 (VEGFR-1), VEGFR-2, and Tie-2, (IC₅₀ of 3, 4, 22nM, respectively). ESK981 treatment potently inhibited HUVEC capillary tube formation and aortic ring explant angiogenesis *in vitro*, and inflammation-induced angiogenesis in Tucker mice and several VEGF-induced angiogenesis models *in vivo*. ESK981 was tested in a dose-escalating Phase I clinical trial to determine its pharmacokinetics and pharmacodynamics in patients with advanced, relapsed, or refractory solid tumors.¹³ ESK981 was acceptably tolerated up to a dose of 97.4 mg/m² (maximum tolerated dose) that was determined to be the recommended Phase II dose. Most adverse events were Grade 1 or Grade 2 and included fatigue, nausea, diarrhea, decreased appetite, abdominal pain, back pain, vomiting, constipation, headache, dizziness, and dyspnea. Grade 3/4 neutropenia was observed in the highest-dose cohorts. More importantly, up to 85% of patients achieved stable disease when measured at ≥6 weeks in cohorts receiving ≥73.0 mg/m².

After Cephalon was acquired by TEVA, further development of the compound was halted due to TEVA's decision to discontinue internal oncology drug development and focus on other therapeutic areas. Due to the exciting data seen in pre-clinical prostate cancer models highlighted in this proposal, Esanik Therapeutics (in which [name] serves on the Scientific Advisory Board) acquired the rights to develop ESK981 in prostate cancer and other indications. To better understand the mechanism of action in prostate cancer, the kinase screen was repeated with modern kinase assays and lower drug concentrations, identifying novel mutant oncogenic kinases inhibited by ESK981 at single digit nanomolar potency. The new screen also confirmed the potency of ESK981 against TKs involved in angiogenesis, as well as a number of other kinases involved in cancer processes including PDGFRA, PDGFRB, RET, FGFR1, FGFR2, AURKA, and AURKB, among others (IC₅₀ of 43, 12, 9, 92, 80, 12, and 17nM, respectively). We carried out a preliminary analysis of the top kinases overexpressed (by RNA-seq) in mCRPC and kinases most inhibited by ESK981 to provide leads to identify the kinase target in mCRPC (Figure 2). Importantly, as our preliminary data will cover, ESK981, at nanomolar levels, induces robust vacuolization associated with activation of the autophagy pathway suggesting that a kinase involved in this pathway was being inhibited. Other MTKIs, such as cabozantinib and crizotinib, did not have this autophagic vacuolization effect even at high micromolar concentrations. *In vitro* data also suggested combined effects with enzalutamide and continued sensitivity in enzalutamide-resistant cell lines. Interestingly, in addition to AR+ prostate cancer cell lines, AR- prostate cancer cell lines were similarly sensitive to ESK981 intimating its potential use in small cell/neuroendocrine variants of prostate cancer. *In vivo*, ESK981 monotherapy inhibited castrated VCaP xenograft growth in a dose-dependent fashion. Tumors from mice treated with ESK981 displayed vacuolization associated with autophagy as well as marked decreases in proliferation (by Ki67 staining).

Interestingly, autophagy is an evolutionarily conserved and orderly process of degradation and destruction of cellular components (Figure 3). As part of this process, double membraned vesicles known as autophagosomes are formed by engulfing cytoplasmic constituents, which then fuse with lysosomes to initiate degradation and recycling.¹ Exaggerated activation of the autophagic process can be observed as gross vacuolization of cells. Monoallelic loss of beclin-1, a gene critical for the autophagy pathway, has been found in 40 to 75% of human breast, prostate, and ovarian cancers.^{1,14} Thus, autophagy has been considered an important tumor suppressive pathway and sustained activation of autophagy in tumor cells leads to apoptosis. A number of approaches to regulate the autophagy pathway are being explored clinically in the treatment of cancer.¹

[figure not shown]

Figure 3. Overview of the autophagy pathway

Adapted from Yang et al.¹ The ULK kinase pathway is the key proximal kinase complex that controls autophagy. It can be regulated by a number of up-stream kinases including receptor tyrosine kinase (RTKs), PI3K, AKT, and TOR. The beclin1 complex is a mediator of autophagy. LC3 processing is a key step in autophagosome maturation. Chloroquine and Bafilomycin A1 block late stage autophagy by blocking lysosomal fusion. ESK981 presumably activates autophagy in CRPC by inhibiting an upstream TK.

1.2.1 Description and mechanism of action

Nonclinical activity

ESK981 is an orally active inhibitor of a number of receptor tyrosine kinases, specifically human TIE-2, VEGFR-1 and VEGFR-2, and FGFR-1, with concentrations resulting in 50% inhibition of activity (IC_{50}) of 22 ± 6 nM, 4 ± 1 nM, 3 ± 1 nM, and 13 ± 2 nM, respectively, in enzyme-based assays. These kinase targets have been shown to have essential and nonredundant roles in tumor angiogenesis and vascular maintenance, and ESK981 is designed to inhibit tumor growth by blocking these processes. ESK981 shows comparable activity against a number of other kinases including tropomyosin receptor kinase (TRK) A (3 nM), TRKB (5 nM), receptor tyrosine kinase (RET) (5 nM), B lymphocyte kinase (BLK) (8 nM), hemopoietic cell kinase (HCK) (13 nM), lymphocyte-specific protein tyrosine kinase (LCK) (12 nM), TGF- β activated kinase 1 (TAK1) (14 nM), and mammalian STE20-like kinase 2 (MST2) (21 nM). Some of these kinases are also known to be involved in tumor growth and survival. ESK981 demonstrates a significant concentration-related activity in a range of experimental systems including VEGF-A, -C, -D-induced, Angiopoietin-1-induced, and fibroblast growth factor-2 (FGF2)-induced human and murine endothelial cell proliferation, chemotaxis, migration, and survival *in vitro*; and microvessel outgrowth and branching in primary rat aortic ring explant cultures *ex vivo*.

Preclinical studies

Significant oral anti-angiogenic efficacy has been observed in VEGF-A-induced, tumor-induced and inflammation-induced neo-vascularization models in rodents. Sustained dose-related anti-tumor activity has been demonstrated with ESK981 *in vitro* across a panel of human and murine tumor cell lines. Significant dose-related and exposure driven *in vivo* anti-tumor efficacy is observed with ESK981 in multiple subcutaneous (melanoma, glioblastoma, breast carcinoma, prostate carcinoma) and orthotopic human and rodent solid (colon carcinoma, renal carcinoma, and glioblastoma) and hematologic (acute leukemia) tumor xenograft models in normal and immunocompromised hosts. Depending upon tumor models with differing dosing regimens, ESK981 exhibits dose-related tumor growth inhibitory and anti-angiogenic effects as well as sustained partial and complete tumor regressions when administered as monotherapy. Specific intermittent oral dosing schedules (drug dosing/drug holidays) of ESK981 using once daily (qd) and twice daily (bid) dosing regimens demonstrate significant anti-tumor efficacy (tumor growth inhibition and partial and complete regressions). In both solid and hematologic tumor models, however, qd and bid continuous administration are optimal. ESK981 is generally well tolerated when administered chronically with cytotoxic agents (e.g., temozolomide [TMZ]) and the combination of ESK981 with TMZ conferred a significant benefit on median survival of orthotopic human glioblastoma-bearing animals relative to that achieved with TMZ alone. In a series of pharmacologic anti-tumor and anti-angiogenic studies conducted in various murine strains, the maximum tolerated dose of ESK981 is 60 mg/kg/day or higher in syngeneic, nude, and severe immunocompromised mice (SCID) mice, and 30 mg/kg/day or higher in nonobese diabetic/severe immunocompromised mice (NOD-SCID) severely immunocompromised tumor-bearing mice.

Phase I open-label, dose-escalating study pharmacokinetics

ESK981 was tested in an open-label dose-escalating Phase 1 clinical trial to determine its pharmacokinetics (PK) and pharmacodynamics (PD) in patients with advanced, relapsed, or refractory solid tumors (Study C11981/1047/ON/US, NCT00875264).¹³ After daily oral

administration of ESK981 to cancer patients, the median t_{max} values for ESK981 were typically in the range of 2 to 4 hr. (Table 1 and Table 2); however, for most of the dose groups there appeared to be considerable inter-patient variability in this pharmacokinetic parameter. The reason(s) for the large inter-patient variability in t_{max} is (are) not presently known, but may be related to the fed/fasted state of the patients or other unknown factors which could potentially influence drug absorption (e.g., disease state, concomitant medications).

Table 1. Mean (SD) Pharmacokinetic Parameters for SK981 in Cancer Patients on Day 1 of Daily Oral Administration of ESK981

Dose (mg/m ²)	C _{max} (ng/mL)	t _{max} ^a (hr)	AUC ₀₋₂₄ (ng·hr/mL)	AUC _{0-∞} (ng·hr/mL)	t _{1/2} (hr)	R _{pred}
3.0 (n=3)	13.7 (6.1)	6.0 [2.0-6.1]	127 (16)	151 (36)	8.0 (2.8)	1.2 (0.2)
4.2 (n=3)	16.8 (4.9)	4.0 [1.0-6.0]	119 (14)	136 (6)	7.8 (3.7)	1.2 (0.1)
5.9 (n=5)	26.0 (6.5)	2.1 [1.5-4.0]	195 (67)	210 (78)	5.9 (1.1)	1.1 (0.1)
11.8 (n=3)	84.9 (23.0)	1.6 [1.5-3.0]	517 (126)	569 (196)	6.0 (3.7)	1.1 (0.1)
19.7 (n=3)	135.7 (76.5)	4.0 [1.0-4.3]	874 (358)	928 (408)	5.1 (1.3)	1.0 (0.1)
29.6 (n=4)	266.9 (182.0)	2.3 [1.0-3.1]	2376 (2064)	3195 (3199)	8.5 (5.5)	1.2 (0.2)
41.4 (n=3)	351.9 (94.4)	2.0 [1.0-4.0]	2820 (2070)	3572 (3177)	8.1 (4.5)	1.2 (0.2)
55.0 (n=4) ^b	272.6 (127.5)	3.0 [3.0-3.2]	2274 (666)	2675 (508)	8.9 (2.5)	1.2 (0.1)
73.0 (n=3)	444.2 (149.4)	4.0 [3.0-4.1]	3939 (1966)	4659 (2634)	8.1 (2.2)	1.2 (0.1)
97.4 (n=9)	526.4 (185.7)	4.0 [2.0-6.0]	5320 (1459)	6915 (2115)	10.3 (4.6)	1.3 (0.3)
126.6 (n=2)	751.2 (780.5, 721.9)	5.0 [8.0, 2.0]	5767 ^d	NC	NC	NC
Overall Mean ^c	-	-	-	-	8.0 (3.7)	1.2 (0.2)

^aValues presented for t_{max} are the median [range]; ^bExcludes data from patient 1019 due to receipt of improper dose of study medication; ^c Overall mean for all dose groups; ^dn=1.

NC: Not calculable.

R_{pred} = AUC_{0-∞}/AUC₀₋₂₄.

Table 2. Mean (SD) Pharmacokinetic Parameters for ESK981 in Cancer Patients on Day 15 of Daily Oral Administration of ESK981

Dose (mg/m ²)	C _{max} (ng/mL)	t _{max} ^a (hr)	AUC _τ (ng·hr/mL)	t _{1/2} (hr)	R _{obs}	R _{ss}
3.0 (n=3)	16.1 (2.3)	2.9 [1.5-4.0]	165 (83)	8.0 (2.9)	1.3 (0.6)	1.1 (0.5)
4.2 (n=3)	24.3 (9.2)	3.9 [1.5-4.0]	202 (47)	9.9 (4.6)	1.8 (0.6)	1.5 (0.4)
5.9 (n=5)	32.4 (8.4)	3.0 [1.5-6.0]	278 (69)	6.6 (1.5)	1.5 (0.6)	1.4 (0.6)
11.8 (n=3)	98.1 (5.6)	2.0 [1.6-2.1]	764 (128)	12.3 (9.7)	1.5 (0.2)	1.4 (0.3)
19.7 (n=3)	128.5 (98.4)	4.0 [1.5-4.0]	1102 (735)	5.4 (1.2)	1.2 (0.3)	1.1 (0.2)
29.6 (n=4)	218.8 (130.3)	4.5 [2.0-8.0]	2924 (2940)	8.7 (5.7)	1.1 (0.2)	0.9 (0.1)
41.4 (n=3)	412.6 (93.9)	2.1 [1.7-3.1]	3256 (1816)	10.3 (6.3)	1.3 (0.5)	1.1 (0.5)
55.0 (n=4) ^b	320.7 (75.1)	5.2 [3.0-8.0]	4313 (1091)	12.8 (4.3)	1.9 (0.2)	1.6 (0.1)
73.0 (n=2)	713.0 (734.5, 691.6)	3.3 [3.5, 3.1]	9429 (12253, 6605)	13.9 (20.6, 7.2)	1.9 (2.0, 1.8)	1.7 (1.6, 1.7)
97.4 (n=7)	7431.3 (336.7)	2.7 [1.5-6.0]	6623 (3283) ^d	11.0 (6.2) ^d	1.5 (0.9) ^d	1.2 (0.7) ^d
126.6 (n=1)	1481.5	8.0	23565	14.7	NC	NC
Overall Mean ^d	-	-	-	9.9 (5.3)	1.5 (0.5)	1.3 (0.5)

^aValues presented for t_{max} are the median [range]; ^bExcludes data from patient 1019 due to receipt of improper dose of study medication; ^c Overall mean for all dose groups; ^dn=6.

R_{obs} = AUC_τ/AUC₀₋₂₄, day 1.

R_{ss} = AUC_τ/AUC_{0-∞}, day 1.

After reaching peak plasma levels, ESK981 declined in a bi-phasic manner that was characterized by an initial phase of drug distribution and a slower terminal elimination phase. For some profiles, however, only the later phase was evident due to what appeared to be a more prolonged period of drug absorption. The mean t_{1/2} of the terminal elimination phase was generally in the range of approximately 8 to 10 hr; however, the

values tended to be slightly larger after multiple doses at the higher dose levels (i.e., doses $\geq 55 \text{ mg/m}^2$) (Table 1 and Table 2).

The systemic exposures (i.e., C_{\max} and AUC) of patients to ESK981 generally increased with increasing dose across the dose range evaluated on both days 1 and 15 (Table 1 and Table 2). There were some dose groups for which the mean values of C_{\max} and AUC did not show an increase relative to the values from the preceding 1 or 2 dose levels; however, this result was not surprising given the large inter-patient variability and the fact that most dose increments were less than 40%. Nonetheless, the overall results obtained are not suggestive of the presence of any obvious non-linearity in absorption and/or elimination of ESK981 in this dose range.

After once-daily administration of ESK981 at doses ranging from 3.0 to 126.6 mg/m^2 , there was a small to moderate amount of accumulation of the compound in plasma at each dose level. The overall mean observed accumulation ratio (R_{obs}) for ESK981 was 1.5 (range = 1.1 to 1.9), which was slightly larger than the value predicted from the single-dose data (overall mean $R_{\text{pred}} = 1.2$; range = 1.0 to 1.3) (Table 1 and Table 2). Although the mean R_{obs} was slightly larger than the R_{pred} , this is not believed to be a strong indication of the presence of any time-dependent pharmacokinetic processes.

1.3 Rationale

ESK981 has cleared a dose-escalating Phase I clinical trial and demonstrated favorable pharmacokinetics and pharmacodynamics in patients with advanced, relapsed, or refractory solid tumors with up to 85% of patients achieving stable disease at doses $\geq 73.0\text{ mg/m}^2$. In our preliminary studies, ESK981 appears to induce robust vacuolization associated with activation of the autophagy pathway in prostate cancer *in vitro* and *in vivo* and demonstrated dose-dependent inhibition of castrated VCaP xenograft growth (Figure 5).

Figure 5.

ESK981 inhibits castrated VCaP tumor growth. Castrated VCaP-bearing mice received vehicle or ESK981 (60 or 30mg/kg) as indicated. A, Tumor volume was measured twice per week over a 25-day course. B, Tumor weight was measured for each group after surgical resection.

Thus, we are conducting a focused open-label Phase II study of ESK981 in men with mCRPC. The study will evaluate men with mCRPC who have progressed on enzalutamide and/or abiraterone acetate. Consenting patients will undergo a biopsy at baseline and after 8 weeks of treatment to assess gene expression and biomarkers. The primary objective will be to determine the PSA \geq 50% response rate (PSA50) from baseline using the Prostate Cancer Working Group 3 (PCWG3) criteria to ESK981 as a single agent.

Currently, CRPC patients receive either enzalutamide or abiraterone acetate as front-line treatment for mCRPC without visceral metastases. If a patient has metastatic disease with visceral metastases he may also receive chemotherapy such as docetaxel. This study explores if ESK981, administered 5 days on and 2 days off can induce a high PSA response rate and/or if AR expression is induced or enhanced from baseline following a standard front-line treatment to determine the PSA50 response rate to ESK981.

1.4 **Rationale for Correlative Studies**

1.4.1 Autophagy induction

ESK981 demonstrated a unique autophagy induction property in our pre-clinical *in vitro* and *in vivo* models through provoking robust cellular vacuolization. Thus, autophagy can serve as biomarker for patient response to ESK981 treatment.

1.4.2 Angiogenesis inhibition

Considering ESK981's anti-VEGFR-A property and our *in vivo* preliminary data that ESK981 strongly attenuated angiogenesis, we believe that angiogenesis can be a biomarker for patient response to ESK981 treatment.

1.4.3 Phosphorylation reduction

According to the kinase inhibition profile data from ESANIK, ESK981 inhibits a group of kinases that have been validated in our preliminary *in vitro* models. Using immunohistochemistry (IHC) to determine phosphorylation levels of these targets can help to assess ESK981 pharmacodynamics in patient.

1.4.4 Tumor cellular proliferation rate

Preliminary data have shown that ESK981 significantly inhibited tumor cell proliferation *in vitro* and *in vivo* xenografts. Therefore, we believe that determining proliferation rate by Ki67 IHC will also be a potential biomarker for patient response to ESK981 treatment.

1.4.5 Other potential markers

Overall patient survival, assessment by radiography, radiographic progression free survival, and PSA progression free survival can be monitored clinically as surrogates for treatment outcomes. Mutation analysis by whole genome sequencing, immunohistochemistry to quantify PD-1 and PD-L1 expression and presence of CD8+ tumor infiltrating lymphocytes can be useful in exploratory evaluation. In addition, select genetic and epigenetic characteristics of the patients' tumors will be assessed as surrogate biomarkers for clinical benefit. These evaluations are expected to identify genomic correlates of response (biochemical recurrence, onset of pain), complications (osteoblastic lesions in bone, cachexia), and survival. The specific biomarker candidates were identified based on their inclusion in either of the following actionable/informative categories: (i) immediate link with the ESK981 mechanism of action, (ii) high prevalence in mCRPC and/or routine clinical testing, (iii) potential less-invasive detection in biofluids. Respectively, the proposed correlative endpoints include expression levels of ESK981 target kinases, ETS-status, and AR amplification/levels in circulating tumor cells. The rationale for each biomarker choice and correlative assessment is listed in section 1.4, while methodological and statistical considerations for the genomic screening are reviewed in section 11.3.

2. **OBJECTIVES**

2.1 **Primary Objective**

The primary objectives of this study are:

- To determine the PSA $\geq 50\%$ response rate (PSA50) from baseline using the PCWG3 criteria to ESK981 as a single agent in men with mCRPC who have progressed on enzalutamide (an oral androgen-receptor inhibitor) and/or oral abiraterone acetate (an androgen synthesis inhibitor).
- To assess the safety and tolerability of ESK981 as a single agent. Adverse events of all grades will be captured by the National Cancer Institute - Common Terminology Criteria for Adverse Events, version 4.03 (NCI-CTCAE v4.03) and GCP standards.

2.2 **Secondary Objectives**

- To determine the time to PSA response to ESK981 in mCRPC patients.
- To determine the duration of PSA response to ESK981 in mCRPC patients.
- To determine PSA progression rates as defined by the PCWG3 criteria.
- To determine PSA progression free survival as defined by the PCWG3 criteria

2.3 Correlative/Exploratory/Tertiary Objectives

- To assess exploratory biomarkers from blood and tumor biopsies. Examples of these may include, but are not limited to: whole exome sequencing, capture whole transcriptome analysis, AR and ARv7 analysis, ki-67, apoptosis, etc.

3. PATIENT SELECTION

A total of 27 patients with mCRPC will be included in this study.

Each subject will be counseled by a study investigator about the planned study procedures, risk and benefits of participating in the study, and alternative therapeutic options. Each subject must sign an Institutional Review Board (IRB)/ Independent Ethics Committee (IEC)-approved consent form and written authorization to use protected health information as outlined in the Health Insurance Portability Act (HIPAA) of 1996, prior to the initiation of any study related procedures.

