11.3 Design

11.3.1 We will utilize a single group single-stage Phase II design for the study. Patients will receive 160mg (4 capsules) of ESK981 dosed once daily for five consecutive days followed by a two consecutive day treatment break, for a cycle of 28 days. After 8 weeks (2 cycles) of ESK981, patients will be evaluated for their rate of PSA decline of $\geq 50\%$ from baseline (PSA50), using the PCWG3 criteria. Extrapolating from the data summarized on PSA50 response at any time by Cheng et al,¹⁶ we hypothesize that the 8-week PSA50 rate in patients similar to patients eligible for this protocol is approximately 20%. We also hypothesize that the 8-week PSA50 rate for ESK981 treated patients will be approximately 30%.

11.3.2 We seek preliminary evidence that the true 8-week PSA50 rate for patients on ESK981 exceeds the hypothesized reference value of 20%. Having a directional hypothesis, the PSA50 rate will be estimated with a 1-sided Wilson type 90% lower confidence interval (CI). With precision defined as a CI half-width (distance from the PSA50 estimate to the lower 90% confidence limit (CL)) of 0.100, a sample size of N=27 patients and a sample estimate of PSA50 = 30% would have a lower CL = 0.201. This would indicate that the true 8-week PSA50 rate was $> 20\%$, with 90% confidence.

11.3.3 The required sample size of N=27 was determined from the "Confidence Intervals for One Proportion" program within the PASS 15 software.¹⁷

11.3.4 Sample size adjustment for non-compliance will be made as follows. A major goal of this study is to evaluate the efficacy (in addition to the effectiveness) of ESK981 upon the PSA50 rate, safety, and tolerability. For each individual patient, we will allow for an ESK981 treatment non-compliance of up to 25% (i.e., up to 25% of pills were not taken).

Our initial analytic focus will be on the patients who are eligible (per Section 3), and evaluable (i.e., were on treatment for at least Cycle 1 [28 days]), and compliant (took at least 75% of the intended ESK981 pills during Cycle 1).

The patients meeting all 3 such requirements will be considered the eligible, evaluable, and compliant ("EEC") subset. We anticipate that up to 15% of the enrolled patients will not become EEC for one reason or another.

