11.5 Expected Accrual Rate, Accrual Duration, and Total Study Duration

- 11.5.1 This will be a clinical trial involving Karmanos Cancer Institute (KCI) only. We expect to accrue 10-12 patients/year.
- 11.5.2 At that rate, we can accrue 32 patients (to obtain 27 EEC patients) in 32-38 months. Allowing an additional 4 months to finish determining all biomarkers and correlatives in all patients yields an estimated total study duration of 36-42 months.

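### Section 3 gives 27 as the total number of patients, but Section 11 needs up to 32 enrolled to obtain 27 analysable patients

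*Combined protocol and SAP*

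**What the plan says.** Section 3 (Patient Selection) opens with "A total of 27 patients with mCRPC will be included in this study". It does not define inclusion, mention attrition or refer to Section 11.

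Section 11.3.2 sets the precision aim: "With precision defined as a CI half-width (distance from the PSA50 estimate to the lower 90% confidence limit (CL)) of 0.100". It then says that "a sample size of N=27 patients and a sample estimate of PSA50 = 30% would have a lower CL = 0.201" and concludes that the true rate would exceed 20% with 90% confidence. Section 11.3.3 attributes the required N of 27 to the PASS software.

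Section 11.3.4 says whom the 27 counts. "Our initial analytic focus will be on the patients who are eligible (per Section 3), and evaluable" for at least Cycle 1, and who took at least 75% of their Cycle 1 pills. This is the EEC subset. The section expects up to 15% of enrolled patients not to reach it, and so enrols up to 27/0.85 = 32. Analyses of patients outside the EEC subset are described as sensitivity analyses. Section 11.5.2 agrees: "we can accrue 32 patients (to obtain 27 EEC patients) in 32-38 months".

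**The concern.** The same number does two jobs. In Section 3 it is the number of patients in the study. In Section 11 it is the number left after attrition. Both hold only if nobody is lost, and Section 11 plans for losses.

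Section 3 cannot safely be read as counting EEC patients. Its sentence stands just before the consent and eligibility text, whereas EEC status is known only after 28 days on treatment and a pill count. No section says that lost patients are replaced. Someone taking the enrolment total from Section 3 would work to 27, five fewer than Section 11 plans, and the main efficacy analysis could then fall short of its stated precision. Conversely, patients 28 to 32 could look like enrolment beyond the Section 3 total.

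**Working it through.** **Inputs.** Total of 27 (Section 3). Required N of 27 EEC, estimate of 30%, one-sided 90% Wilson lower limit, half-width target 0.100, reference rate 20% (Section 11.3.2). Attrition up to 15% and enrolment of up to 32 (Section 11.3.4). Accrual of 10-12 patients a year (Section 11.5.1).

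**Formula.** With z = 1.2816 (one-sided 90%), the Wilson lower limit without continuity correction is

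L = [p + z²/(2n) − z·√(p(1−p)/n + z²/(4n²))] / (1 + z²/n), and the half-width is p − L.

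**Step 1: reproduce the plan's figure (n = 27, p = 0.30).** z² = 1.6424, so z²/(2n) = 0.03041. The square root is √(0.007778 + 0.000563) = 0.09133, and 1.2816 × 0.09133 = 0.11704. L = (0.30 + 0.03041 − 0.11704)/1.06083 = 0.2011, with half-width 0.0989. This matches the stated 0.201 and meets the 0.100 target. The continuity-corrected form gives 0.186 and does not match, so the plan used the uncorrected form.

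**Step 2: reproduce the enrolment figure.** 27/0.85 = 31.76, rounded up to 32. Accrual of 32 at 12 a year takes 32.0 months, and at 10 a year 38.4 months, in line with the stated 32-38. Section 11 is internally consistent.

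**Step 3: follow Section 3 instead.** 27 × 0.85 = 22.95, about 23 EEC patients. For n = 23: L = (0.30 + 0.03570 − 1.2816 × 0.09953)/1.07141 = 0.1943, with half-width 0.1057.

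| EEC patients | Lower limit at 30% | Half-width | Half-width at most 0.100? |
|---|---|---|---|
| 27 | 0.2011 | 0.0989 | yes |
| 26 | 0.1996 | 0.1004 | no |
| 25 | 0.1979 | 0.1021 | no |
| 23 | 0.1943 | 0.1057 | no |

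So 27 is the smallest n that meets the target, and it has no reserve. The miss at 26 is only 0.0004.

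**Step 4: chance of reaching 27 EEC.** Assume that patients qualify independently with probability 0.85, the least favourable rate in the plan. With 27 enrolled, all must qualify: 0.85^27 = 1.2%. With 32 enrolled, the binomial chance of at least 27 is 65%.

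**Step 5: whole patients.** A 30% estimate is not attainable at n = 27 (0.30 × 27 = 8.1) or at n = 23 (6.9). The attainable results nearest 30%, and the smallest that exclude 20%, are:

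| EEC patients | Nearest 30% | Lower limit | Smallest result excluding 20% | Lower limit |
|---|---|---|---|---|
| 27 | 8/27 = 29.6% | 0.198 | 9/27 = 33.3% | 0.230 |
| 23 | 7/23 = 30.4% | 0.198 | 8/23 = 34.8% | 0.235 |

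The observed rate needed to exclude 20% rises by 1.5 percentage points. If the true rate is 30%, the binomial chance of excluding 20% is 42% at n = 27 (9 or more responders) and 38% at n = 23 (8 or more).

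**The case against.** The strongest reply is that this is a lagging sentence and not a design fault. Section 3 probably repeats the statistical N without the attrition note, while the two sections that govern sample size and accrual are explicit and agree on 32. Harm arises only if Section 3 is followed in preference to them. That is fair, and it limits the weight of the point. It does not reconcile the two totals.

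A reader might infer more than the documents support, in four ways:

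- **That Section 3 caps enrolment.** It states a total. It gives no maximum and no stopping rule.
- **That the main analysis will have 23 patients.** The 15% is an upper bound. With no attrition, 27 enrolled would be enough.
- **That the trial's success scenario works at 27 and fails at 23.** The contrast of 0.201 with 0.194 exists only at exactly 30%, which neither size can produce. The nearest attainable result fails at both, with the same lower limit of 0.198. Nor does losing one to three patients lower the chance of excluding 20%. At a true rate of 30% it is 54%, 49% and 44% at n = 26, 25 and 24, against 42% at 27, because 8 responders suffice instead of 9. Part of that gain is bought with false positives: at a true rate of 20%, the chance of 8 or more responders among 26 is 13.1%, against 7.4% for 9 or more among 27.
- **That the monitoring report form in Appendix F is wrong.** It is a blank template whose accrual-goal field holds no figure.

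What stands is the conflict between the totals, and the fact that the stated 0.100 precision at a 30% estimate is not met with fewer than 27 EEC patients.

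**Conclusion.** The point holds as an inconsistency between sections. Section 3 gives 27 as the study total; Sections 11.3.4 and 11.5.2 give 27 as the EEC requirement and up to 32 as enrolment. It is not a calculation error, since every Section 11 figure checked here reproduces.

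At the stated maximum attrition, following Section 3 would leave about 23 EEC patients and a half-width of 0.106 against the 0.100 target. That is a small loss of precision in a study seeking preliminary evidence, and the practical bar barely moves. It should still be corrected, because a sample size the trial relies on is stated in two incompatible ways.

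The size of the effect rests on three assumptions: the EEC subset is the main efficacy set, as Section 11.3.4 says; attrition is at its 15% upper bound; and precision is judged at a 30% estimate, as in Section 11.3.2. The chances of reaching 27 EEC patients also assume that patients qualify independently.

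**What to change.** Replace the Section 3 sentence with: 'Up to 32 patients will be enrolled to obtain 27 EEC patients (Section 11.3.4).' Sections 11.3 and 11.5 need no change on this point, and neither does the Appendix F template.

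The cost is one sentence in an amendment. The 32 patients and the 32-38 month accrual period are already in the plan, so no patients or time are added, and no eligibility criterion or analysis changes.
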